5.0 STUDY PROCEDURES

This project was designed to seamlessly integrate with the current pathway and standard of care both surgically and with medical oncology treatments. The patient will be evaluated in [name] clinic and discussed with Drs. [name], [name] and [name] in the weekly multi-disciplinary conference from 12-1 pm every Thursday. Suitable patients will be invited to participate in this research by someone involved in their care. Those interested in participating will be referred to a member of [name] research team. Patients enrollment in the UWCCC Biobank program will be conducted in accordance with the Biobank protocol.

Subjects will obtain standard of care (SOC) labs and pre-operative imaging as well as research PSMA-PET imaging prior to surgery. Surgery will proceed as per SOC and will not have extra procedures specific to this project. Patients will have time to recover following surgery and receive SOC imaging. Metastatic RCC patients will have a 2nd PSMA-PET (PET2A) greater than 4 weeks post-surgery and prior to initiation of systemic therapy. Patients with locally advanced disease will not have PET2A until metastatic RCC identified with SOC imaging. The rationale for the second PSMA PET prior to start of systemic therapy (PET2A) is to establish a new baseline PET. We want to establish any potential post-surgical PET findings from PET1 to PET2A (ex: post-surgical PET changes, change in PSMA PET uptake at sites of remaining measurable disease, new potential lesions). This will be followed by a third PSMA PET (PET2B) obtained at 12-16 weeks from start of first-line SOC systemic therapy, either immune-based and/or anti-angiogenesis therapy (with associated SOC conventional diagnostic chest/abdomen/pelvis CT) to evaluate mRCC tumors response to treatment. This time point is chosen given that less than 10% of patients will have progressive disease on SOC conventional imaging at their initial evaluation.

If the first line SOC systemic therapy did not include an anti-angiogenesis therapy and if this second systemic therapy includes anti-angiogenesis therapy, an additional 4th and 5th PET imaging will be obtained as PET3A and PET3B. PET3A is obtained prior to start of additional systemic therapy including anti-angiogenesis therapy, to establish a new baseline PET before this systemic therapy commences, to characterize the existing metastatic tumors and any metastatic tumors which develop between PET2B and start of this systemic therapy. PET3B is obtained at 12-16 weeks from start of this second systemic therapy including anti-angiogenesis therapy (with associated SOC conventional diagnostic chest/abdomen/pelvis CT) to evaluate mRCC tumors response to treatment.

Following recovery from surgery the patients will initiate systemic therapy as per SOC. The patients will receive systemic therapy with an antiangiogenic agent as per first-line or later SOC therapy. There are currently 4 oral antiangiogenic agents approved by FDA for the treatment of patients with metastatic RCC (pazopanib, sunitinib, cabozantinib, axitinib) and patients on this study will receive one of those 4 agents as per physician's preference.

Study procedures will include a tissue analyses as well as the use of PET/CT imaging to monitor subject's clinical response to treatment. For tissue, immune cell and CTC analyses, investigators will be working with the UWCCC Biobank staff to acquire blood samples and tissue samples donated from the kidney with primary tumor, lymph nodes, and any other metastatic site from which tissue was collected.

Subjects will be asked to complete four to six research visits that will include the administration of a PSMA PET/CT exam. There will be an initial baseline ¹⁸F-DCFPyL PSMA PET/CT (PET1) prior to nephrectomy and SOC biopsy of metastatic sites as clinically indicated, followed by a second ¹⁸F-DCFPyL PSMA PET/CT (PET2A) prior to start of systemic anti-angiogenesis and/or immune-based therapy. A third on-treatment ¹⁸F-DCFPyL PSMA PET/CT (PET2B) will be performed at 12-16 weeks from start of systemic therapy (with associated SOC diagnostic chest/abdomen/pelvis CT). If system The fourth (or sixth if there is PET3A and PET3B) ¹⁸F-DCFPyL PSMA PET/CT (PET4) will be performed at the time of disease progression as determined by conventional imaging such as CT or MRI; or two years after initiation of therapy (whichever one comes first).

Blood and Tissue Collection

We are collaborating with the UWCCC Translational Science BioCore (TSB) for sample collection as this research is consistent with their mission "to facilitate cancer-related basic science and translational research within the UWCCC through the integration of human biospecimen collection and storage with associated histology, molecular, morphometric and consultative services". The TSB team is uniquely equipped to appropriately identify and consent patients and to collect and properly handle/process the samples without disrupting the clinical workflow. As a result, this research will only target patients that have previously consented to allow additional and residual tissue samples to be included in the UWCCC Biobank. Biobank personnel will provide blood and the sample(s) collected from the kidney with primary tumor, lymph nodes, and any metastatic sites that are excised.

PET/CT Imaging

Each PET/CT research visit is estimated to take 2-3 hours to complete. Women of childbearing potential will be administered a pregnancy test prior to the start of imaging procedures. Subjects will be asked to fast for 4 to 6 hours and to stay well hydrated prior to each visit. Upon their arrival to the WIMR facilities, an IV will be placed to allow injection of the PET tracer. After the IV administration of less than 9 mCi of ¹⁸F-DCFPyL radiotracer by slow IV push, subjects will be required to sit quietly for 1-hour to allow for the biodistribution of the tracer. After approximately 50 minutes, subjects will be given the option of using the restroom prior to being positioned in the PET/CT scanner. Once positioned, a whole body (defined in this protocol as vertex-of-skull to mid-thigh) PET scan will be obtained with corresponding low-dose non-IV contrast CT imaging with the PET/CT obtained for PET attenuation correct and anatomic co-registration.

A member of the study team will follow-up with all subjects approximately 1 to 3 days after their PET/CT exam by phone to inquire about delayed adverse events. If the subject is experiencing any late occurring adverse events, they will be asked to return to the research clinic or urology clinic for a follow-up exam.

Review of Medical Records

Medical records will be reviewed to obtain medical history including physical exams, medications (all concomitant medications before and after each of the PET/CT scans, treatment medications for RCC), laboratory tests (metabolic chemistry, hematology, pathology), imaging results (all available CT, MRI, ultrasound, PET/CT) and information related to the diagnosing, treatment, or outcomes of the study subject's diagnosis, treatment and clinical follow-up up to two years from the time of initiation of systemic anti-angiogenesis therapy.

Remuneration

Subjects will receive \$50 per scan, for a total of up to \$300, as compensation for their participation in this study.

Withdrawal/Termination from Study

Reasons for withdrawal or termination

Enrolled patients will be removed from the study in the following circumstances:

- The patient does not complete the imaging examinations per study protocol
- The subject withdraws consent
- Exclusion criteria are discovered after registration but prior to the research examinations
- The PI or co-investigators determine it is within the best interest of the subject to remove them from the research.

Study Procedures Table

Study Procedures	Screening ¹	Baseline Prior to surgery	VISIT 2a and 2b Prior to and during 1 st systemic therapy	VISIT 3a and 3b Prior to and during 2 nd systemic therapy	VISIT 4 ²
Informed Consent ⁵	X				
Clinical History	X				
PET/CT Exam		X	X ⁴	X ⁴	X
Tissue Collection			X ³		

1. Screening visit may be completed on the same day as the baseline visit
2. To be done at the time of disease progression or within 2 years, whichever occurs first.
3. Tissue collection will occur post SOC surgery and will be coordinated with the UWCCC TSB.
4. PET/CT scan obtained prior to systemic therapy (immune-based and/or anti-angiogenesis therapy) and at 12-16 weeks into therapy
5. During the COVID-19 pandemic, consent procedures will be conducted by phone, when possible, to minimize face-to-face contact subjects have with the research team. An encrypted copy of the consent form will be mailed or emailed to subjects prior to the scheduled consent phone call.

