IND	Investigational New Drug
kg	kilogram
MBq	megabecquerel
mCi	millicurie
mGy	milligray
MicroC ³	microfluidic-cis-co-culture
mL	milliliter
mmol	millimole
mRCC	Metastatic Renal Cell Carcinoma
PACS	Picture Archiving and Communication System
PET	Positron Emission Tomography
PI	Principal Investigator
PSMA	Prostate-specific membrane antigen
RCC	Renal Cell Carcinoma
REM	Roentgen Equivalent Mammal
RF	Radio frequency
RPF	Radiopharmaceutical Production Facility
SAE	Serious Adverse Event
UP	Unanticipated Problem
UW	University of Wisconsin
UWHC	University of Wisconsin Hospital and Clinics

STATEMENT OF COMPLIANCE

The signature below constitutes the approval of this protocol and the attachments, and provides the necessary assurances that this trial will be conducted according to all stipulations of the protocol, including all statements regarding confidentiality, and according to local legal and regulatory requirements and applicable US federal regulations and ICH guidelines.

I agree to ensure that all staff members involved in this study are informed about their obligations in meeting the above commitments.

Principal Investigator: [name]

Signed:

Date:

[name].
Department of Radiology, Nuclear Medicine Section
University of Wisconsin School of Medicine and Public Health
University of Wisconsin Carbone Comprehensive Cancer Center

PROTOCOL SUMMARY

Title	Functional Microscale Organotypic Assays to Predict Patient Response to Anti-Angiogenesis Therapies.
IND Sponsor-Investigator	[name]
Co-Investigators	[name] E. [name] [name]
Participating Site	University of Wisconsin-Madison
Patient Population	Patients diagnosed with metastatic clear cell RCC that are surgical candidates
Accrual Objective	This research will enroll 15 subjects
Study Design	Phase 2, single-center, open-label study
Study Duration	The estimated accrual period is over 3 years
Primary Objective	The primary objective of this research is to evaluate response to systemic therapy, including anti-angiogenesis and/or immune-based therapies, via ¹⁸ F-DCFPyL PSMA-based PET/CT in patients with metastatic renal cell carcinoma and to compare qualitatively with conventional imaging response criteria (RECIST 1.1) and histopathological endpoints including isolation, enumeration and staining of Circulating Tumor Cells (CTC).
Secondary Objectives	1. Measure therapy response of patient specific uVESSEL model 2. Evaluate the predictive power and validate the uVESSEL model

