Inclusion Criteria	
 Patients diagnosed with locally advanced (\geqcT3) or metastatic clear cell RCC, as proven by biopsy. Adults, 18 years of age or older. Surgical candidates who have clinical indication for nephrectomy and standard of care biopsy of metastatic disease followed by possible standard of care systemic anti-angiogenesis based treatment regimen Have consented to participate in the UWCCC Biobank.
Exclusion Criteria	
 Patients who have received prior RCC systemic therapies Prior history of prostate cancer Prior history of any other malignancy within the last 2 years, other than skin basal cell or cutaneous superficial squamous cell carcinoma that has not metastasized and superficial bladder cancer Unable to lie flat during or tolerate PET/CT Serum creatinine $>$ 2 time the upper limit of normal
Treatment Description	¹⁸ F-DCFPyL whole body PET/CT scan administered at the following timepoints: 1) Prior to scheduled nephrectomy 2) After completion of systemic antiangiogenesis and/or immune-based therapy 3) When patient is refractory to treatment
Study Procedures	
 ¹⁸F-DCFPyL whole body PET/CT scan Review of relevant imaging and medical record information
Statistical Considerations	A total of 15 patients will be recruited into the clinical study. This is based on the feasibility and availability of suitable patients over the funding period with

	approximately five patients per year. With 15 patients, the mean of quantitative endpoints such as tumor size and SUV parameters will have standard error that is 0.258 times the sample standard deviation, and the width of a 95% confidence interval for the probability of binary qualitative endpoints such as objective response will be less than 0.253.
--	---

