Study population: A total of 15 patients diagnosed with clear cell RCC will be enrolled in this study. Achieving the objectives outlined above will require the collection of tissue from the UWCCC Biobank, the review of subject medical records, and subject participation in up to four research visits lasting approximately 2 – 3 hours.

Inclusion Criteria:

- Patients diagnosed with locally advanced (\geq cT3) or metastatic clear cell RCC, as proven by biopsy.
- Adults, 18 years of age or older.
- Surgical candidates who have clinical indication for nephrectomy and standard-of-care biopsy of metastatic disease followed by possible standard of care systemic anti-angiogenesis based treatment regimen
- Have consented to participate in the UWCCC Biobank.

Exclusion Criteria

- Patients who have received prior RCC systemic therapies
- Prior history of prostate cancer
- Prior history of any other malignancy within the last 2 years, other than skin basal cell or cutaneous superficial squamous cell carcinoma that has not metastasized and superficial bladder cancer
- Unable to lie flat during or tolerate PET/CT
- Serum creatinine > 2 times the upper limit of normal

Subject identification and recruitment

GU Oncology staff will identify patients who meet the eligibility criteria and will introduce them to this research opportunity. Those interested will be referred to a study team member who will review the purpose of the research as well as details about participation.

Informed Consent and Subject Information

The consent process will occur prior to the administration of research PET/CT procedures. Potential subjects will meet with a study team member to review the information in the consent form including study procedures, risks associated with participation, alternatives to participation and whom to contact for additional information. Any questions will be addressed prior to the start of any study procedures and all subjects will be reminded that participation is optional and they can change their mind at any time.

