10.0 STATISTICAL CONSIDERATIONS

As noted in section 3.0, the primary objective is to evaluate response to anti-angiogenesis therapy using PSMA-based PET. Other endpoints such as qualitative objective response based on RECIST 1.1 and quantitative CT-based tumor size and SUV parameters will also be evaluated. The secondary objectives are 1) to measure therapy response of patient-derived uVESSEL models using multiple endpoints such as vessel sprouting, PSMA expression and cell death and 2) to evaluate the predictive power and validate the uVESSEL model for clinical outcomes.

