10.1 Sample size justification

A total of 15 patients will be recruited into this clinical study. This is based on the feasibility and availability of suitable patients over the funding period with approximately five patients per year. With 15 patients, the width of a 95% confidence interval for the probability of qualitative response based on PSMA-PET and objective response based on RECIST 1.1 will be less than 0.253 and the mean of quantitative endpoints such as CT-based tumor size and SUV parameters will have standard error that is 0.258 times the sample standard deviation.

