10.2 Statistical analysis

Statistical analysis will by necessity (n=15) and nature (predictive modeling of response using patient-derived ex-vivo uVESSEL responses as predictors, among others) be exploratory and descriptive including qualitative comparison between responses based on PSMA-PET and RECIST 1.1 without a formal paired test of statistical significance.

Measures of patient response to anti-angiogenics via clinical endpoint such as response based on PSMA-PET (primary endpoint) and objective response based on RECIST 1.1 and histopathological endpoints (tumor vascular density, immunohistochemical staining for PSMA and neovascularization (CD30, CD34)) will be summarized with descriptive statistics (response rate and confidence interval), and changes in these endpoints, PSMA staining from baseline to end of treatment and follow-up) will also be summarized with descriptive statistics. Measures of tumor neovascularization via PSMA-based PET/CT imaging will be summarized with descriptive statistics over time and analyzed using generalized linear mixed-effects models for longitudinal measures. Qualitative ¹⁸F-DCFPyL PSMA PET/CT imaging will be recorded in a three-point scale, and statistical analysis will be performed with the equivocal score of 1 considered as positive or negative. Histopathological endpoints will be qualitatively graded by our study pathologist on a zero to four scale with four being the highest level of immunohistochemical staining or neovascularization.

Partial responses are likely from conventional clinical imaging in mRCC patients. Standard imaging techniques define responses to therapy based on size changes of target lesions using RECIST1.1. Metastatic tumors may respond to anti-angiogenic treatment but not change substantially in size (unlike cytotoxic therapies for which RECIST was designed). To address this limitation in current imaging, we combine standard imaging with functional imaging protocols to evaluate whether angiogenesis decreases in individual metastatic lesions regardless of changes in tumor size. PSMA PET signal is used as a surrogate for changes in tumor neovasculature. These functional imaging findings will be

confirmed pathologically by evaluating angiogenesis/ PSMA expression in tumor samples and patient models. Using this approach, we will evaluate functional anti-angiogenesis responses to therapies.

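### The 0.253 precision in section 10.1 needs a PSMA-PET response from all 15 recruits; the scan and removal rules do not secure that, and section 10.2 names no denominator

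*Combined protocol and SAP*

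**What the plan says.** **Precision.** Section 10.1 sets the sample at 15 on feasibility grounds and continues: "With 15 patients, the width of a 95% confidence interval for the probability of qualitative response based on PSMA-PET", and likewise for RECIST 1.1 response, will be below 0.253. The Statistical Considerations row of the protocol summary gives the same number for binary endpoints in general: "the width of a 95% confidence interval for the probability of binary qualitative endpoints such as objective response will be less than 0.253". It does not name PSMA-PET.

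**Who is enrolled.** The first inclusion criterion in section 4.0 admits locally advanced disease (cT3 or higher) "or metastatic clear cell RCC, as proven by biopsy". The third describes the later systemic regimen only as possible.

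**Who is scanned.** Section 5.0 states: "Patients with locally advanced disease will not have PET2A until metastatic RCC identified with SOC imaging". Sections 3.1 and 5.0 place PET2B 12 to 16 weeks after first-line therapy starts. They add PET3A and PET3B only when the first line lacked an anti-angiogenic agent and the next line contains one.

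**Who is removed.** The first bullet under Withdrawal/Termination in section 5.0 takes a patient off study for not completing the required imaging. It is silent on replacement and on whether data already collected are kept.

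**What is reported.** Section 10.2 makes PSMA-PET response the primary endpoint and says that such measures "will be summarized with descriptive statistics (response rate and confidence interval"). It does not say which patients form the denominator.

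**The concern.** A response on PSMA-PET needs a baseline scan and an on-treatment scan. The precision statement counts recruits, while the response rate can only count patients who reach both scans. A locally advanced recruit in whom no metastasis is found, or any recruit who starts no systemic therapy, has no such pair. The plan makes no allowance for this.

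Two things are at stake. First, the interval around the primary rate may be wider than section 10.1 leads the reader to expect. Second, the rate itself depends on choices not yet written down: who is counted, which pair is used when there are two, and whether a patient removed for incomplete imaging stays in. If the removal rule is carried into the analysis, the primary rate describes completers only and may leave out patients who died or deteriorated before the scan. PET response is also the dependent variable in the uVESSEL model of section 3.2.2, so the ambiguity carries into a secondary objective.

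**Working it through.** **Inputs.** n = 15 recruits and a 95% interval (section 10.1); an expected response rate of about 30% for pazopanib and sunitinib (section 10.2). The documents give no evaluable fraction, dropout rate or locally advanced share. Section 10.3 gives only a combined 33-50% for locally advanced or metastatic disease among new patients. The evaluable numbers below 15 are therefore assumptions.

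**Step 1: reproduce the plan's figure.** Wald half-width = 1.96 × √(p(1−p)/n). With p = 0.5 and n = 15: 1.96 × 0.5/√15 = 0.2530. The largest value attainable with 15 patients is at 7 or 8 responders, 0.2525, so below 0.253 is correct as a half-width. The full width is 2 × 0.2530 = 0.506. The figure therefore reproduces only as a half-width, with all 15 recruits counted.

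**Step 2: vary the evaluable number.**

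| Evaluable n | Half-width, p = 0.5 | Relative to n = 15, √(15/n) | Half-width, p = 0.3 |
|---|---|---|---|
| 15 | 0.253 | 1.00 | 0.232 |
| 14 (assumed) | 0.262 | 1.04 | 0.240 |
| 13 (assumed) | 0.272 | 1.07 | 0.249 |
| 12 (assumed) | 0.283 | 1.12 | 0.259 |
| 10 (assumed) | 0.310 | 1.22 | 0.284 |

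**Step 3: how many losses 0.253 can absorb.** n needed = 1.96² × p(1−p)/0.253². At p = 0.5 this is 3.8416 × 0.25/0.0640 = 15.0, so no loss is absorbed. At p = 0.3 it is 3.8416 × 0.21/0.0640 = 12.6, so 13 evaluable patients suffice and two can be lost.

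**Step 4: what defines a response.** Sections 3.1 and 5.0 call PET2A and PET3A new baselines, and PET2B and PET3B the scans for judging response. The pairs PET2A/PET2B and PET3A/PET3B are thus implied. A patient with immune-only first-line therapy followed by an anti-angiogenic line can have both, and section 10.2 does not choose between them. The target also shifts: section 3.1 covers any systemic therapy, whereas section 10.0 says "the primary objective is to evaluate response to anti-angiogenesis therapy using PSMA-based PET" and section 10.2 also speaks of response to anti-angiogenics. The mixed-effects models in section 10.2 can use incomplete series of PET measures, but they do not supply a denominator for a binary rate.

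**The case against.** The strongest reply is that section 10.1 is conditional on 15 patients, the sample is feasibility-based, and section 10.2 calls the analysis exploratory and descriptive, so no test or decision depends on the figure. That stands, and it limits the consequence. A rate with an interval still needs a stated denominator.

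Several stronger readings are tempting but not supported:

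- *That the trial will fall well short of 15 responses.* The PET2A rule defers the scan and does not cancel it. The third inclusion criterion also refers to biopsy of metastatic disease, so purely locally advanced recruits may be few. Sections 3.1 and 5.0 expect under 10% to have progressed at first evaluation: below 0.10 × 15 = 1.5 patients, though this covers progression only. No loss is demonstrated.
- *That patients on immune therapy alone fall outside the primary endpoint.* Section 10.0 refers back to section 3.0, which includes immune-based therapy; on that reading PET2A/PET2B counts for them. Section 5.0 also says study patients will receive one of four anti-angiogenic agents. This is an ambiguity to settle, not a rule that excludes anyone.
- *That removed patients' data are discarded.* The removal bullet does not say so. A locally advanced patient not yet due for PET2A has arguably not missed anything.
- *That the scan pairs are undefined.* They are implied; only the choice between two is missing.
- *That the protocol summary promises this precision for PSMA-PET specifically.* It speaks of binary endpoints generally.

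**Conclusion.** The concern holds in a limited form. The 0.253 in section 10.1 is a half-width that assumes 15 response-evaluable patients. The eligibility, scan-timing and removal rules do not secure that number, and section 10.2 leaves the denominator, and the choice between two pairs, open.

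The size depends on an evaluable number the documents do not give. In the worst case a single loss breaks the bound (0.262 at 14), and at 10 evaluable patients the interval is about 22% wider. At the plan's own 30% rate the bound survives down to 13. A reader might infer a biased primary rate, but neither its size nor its direction can be derived, and none is claimed. No error rate or power is affected. The 0.258 standard-error factor is untouched for PET1 baseline means if all 15 are scanned, and RECIST response may still be available from standard imaging when a research PET is missed. This should be corrected before analysis, but it does not undermine the study.

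**What to change.** 1. **Section 10.1, and the protocol summary for consistency.** Label 0.253 a half-width, say that it assumes 15 response-evaluable patients, and give it for a range such as 15, 14, 12 and 10, marked as assumptions.
2. **Withdrawal/Termination, first bullet.** Reword so that a missed scan ends or skips research imaging only. Data already collected and record follow-up are kept and analysed unless consent for their use is withdrawn.
3. **Section 10.2.** Define the response denominator as patients with metastatic disease who start the systemic therapy of interest, reconciling section 3.1 with sections 10.0 and 10.2 on which therapy that is. Designate the pair that counts when both exist. Report the number of missing pairs and the reasons. Add a sensitivity rate in which patients with no on-treatment PET because of death or deterioration count as non-responders.

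The cost is protocol wording, a less favourable stated precision and one extra descriptive rate. No additional patients or scans are needed.
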